4.1 Dose Limiting Toxicity

DLT evaluable subjects include:

- Part I: All subjects
- Part II: The first three (or six if there is one DLT in the first three) subjects in the following cohorts
 - Q3W cohorts at dose levels that have not previously been tested in Part I
 - Q2W cohorts at each new dose level for the Q2W schema
 - Q1W cohorts at each new dose level for the Q1W schema
- Part III: DLT not applicable

DLT assessment period in Part II is shorter than in Part I, justified by the safety and tolerability data collected during the trial and enabling prompt dose escalation as a part of the 3+3 design of Part II.

- Part I: 63 days (9 weeks) following the first dose of FP-1305
- Part II: 28 days (4 weeks) following the first dose of FP-1305

A DLT is defined as a drug related AE \geq Grade 3 according to NCI-CTCAE version 5.0 occurring during the DLT assessment period and related to FP-1305. The following are exceptions to the rule:

- Grade 3 infusion reactions that resolve within 8 hours from the onset of the reaction are not defined as a DLT
- Grade 3 nausea/vomiting or diarrhea for less than 72 hours with adequate antiemetic and other supportive care are not defined as a DLT
- For thrombocytopenia, haemorrhage is required to qualify grade 3 toxicity as DLT; Grade 4 thrombocytopenia is DLT regardless of haemorrhage
- For neutropenia DLT is as follows,
 - Any neutropenic fever
 - Grade 3 neutropenia persisting $>$ 5 days or Grade 4 neutropenia
- For toxicity judged to be consistent with an acute infusion-related reaction or cytokine release syndrome, DLT will be defined as follows (Sehn 2012):
 - Grade 4 drug-related AE or
 - Grade 3 drug-related AE that cannot be resolved by infusion rate reduction or interruption, or supportive care.
- An AE which, in the opinion of the Investigator, is attributed to a study subject's underlying disease will not be considered a DLT.

In addition, the following are considered DLTs (occurring during the DLT assessment period and related to FP-1305):

- Grade ≥ 2 ALT or AST increase accompanied with bilirubin elevation $>2x$ ULN if baseline value was normal; $>2 \times$ baseline if baseline value was abnormal
- Dose delay of the 2nd cycle due to drug-related toxicity of >14 days

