4.3.2 Dosing Rules (30 - 100 mg/kg) (Q3W, Part II)

Sentinel dosing will be applied for 30-100mg/kg dosing. The second subject on a particular dose level can receive the first dose only after the first subject has been followed up for 28 days (additional precaution compared to traditional 3+3 model) after the first dose, and has not demonstrated any DLT. The third subject may receive the first dose after the second subject has been followed up for 28 days after the first dose and and neither of the subjects have demonstrated any DLTs. DLT evaluable subject will have at least one dose of IMP and have at least 28 days of follow-up after IMP infusion. If these criteria are not met, the subject will be replaced. Once three evaluable subjects have received at least one dose and have been followed up at for 28 days with no DLTs, all remaining subjects on the dose level may be enrolled without any hold. If any of the first three subjects cannot be followed for the full 28-day DLT observation period for reasons other than DLT, the subject may be replaced in order to obtain the required tolerability information of 28 days from the first IMP infusion, before the remaining subjects on the dose level may be enrolled. The replaced subject will, however, count towards the cohort of 10 subjects. The same rules will apply for the other dose levels.

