8.2.1 First Infusion

- The first FP-1305 infusion should be administered I.V. at an initial rate of 50 mL/h for the first 30 minutes.
- In the absence of a hypersensitivity reaction, the infusion rate may be increased gradually as per the instructions given in the Pharmacy Manual. Infusion rate will be limited based on the dosing level and volume of saline utilised.

- If a hypersensitivity reaction develops, the infusion should be temporarily stopped for up to 3 hours. Upon resolution of the subject's symptoms, the infusion can resume at one-half the rate previously associated with hypersensitivity.
- If the subject's symptoms do not resolve within 3 hours, the administration of FP-1305 should be discontinued for this cycle.
- If a second infusion reaction develops despite a reduced infusion rate, the administration of FP-1305 should be discontinued for this cycle.

All subjects in Part I dose-escalation cohorts must be closely monitored for safety for the first 24 hours after the first IMP infusion at the trial site hospital. Subjects in the dose-expansion cohorts in Part I and in Part II must be monitored for a minimum of 6 hours after the first IMP administration. However, first three subjects testing new doses or dosing frequencies in Part II should be closely monitored for safety for the first 24 h after the first IMP infusion at the trial site hospital. In Part III, all subjects must be monitored for minimum of 4 hours after the first IMP infusion. Any subject who is deemed at risk of tumour lysis syndrome or any other safety concern by the judgement of the treating investigator may be hospitalized for a longer period.

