8.7 Dose Modifications, Infusion Delays, Missed Doses and Special Cases

IMP infusion will be prepared based on the subject's predose weight at each cycle (if not available, the most recent weight should be used). No visit specific dose adjustments are allowed for FP-1305, except for weight change adjustments. However, the maximum amount of FP-1305 in one IMP infusion is 10 g and cannot be exceeded irrespective of the weight-based dose. Guidance will be provided in the Pharmacy Manual to ensure calculated doses do not exceed this limit. If the IMP cannot be administered at the scheduled visit for any reason, the IMP must be administered as soon as possible, below here are instructions for Q3W schema. Instructions for Q2W and Q1W schemas are in Protocol Addendum.

- If the delay is 1 to 7 days, the procedures based on the current visit should be performed, and the subsequent visit will follow 21 days from the date of the infusion that occurred.
- If the delay is more than 7 days, the dose is considered missed, and the next per protocol visit should be brought forward and performed as soon as possible. Note, that the tumour images are still to be taken at every scheduled time point
 - (e.g. if there is an eight day delay for Cycle 4 Day 1, Cycle 4 IMP is considered a missed dose. The infusion given eight days after the original schedule in this case is Cycle 5 IMP dose and the related Cycle 5 procedures should be performed. In addition, tumour imaging of Cycle 4 should be done.) The subsequent visit will follow 21 days from the date of the infusion that just occurred.
 - Cycle 2 is an exception: every effort should be made to ensure that Cycle 2 is not delayed. In unavoidable delay, Cycle 2 IMP administration and the related Cycle 2 procedures should be performed as soon as possible.

Subjects that miss two consecutive scheduled doses (more than 49 days from the previous dose) will discontinue the treatment and enter the follow-up period unless specific consultation and agreement occurs between the investigator, the Medical Monitor and the Sponsor justify continued trial therapy. These decisions must be carefully documented.

Additionally, intra-subject dose change may occur to the recommended Part II/Part III dose after it has been determined. This decision must be carefully documented.

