8.9.1 Infusion Reactions

In case of an infusion reaction, the following documentation should be recorded

- 1) Pre-infusion assessment (i.e., the drugs administered, doses, number of previous infusions of the agent, and infusion rates)
- 2) Initial symptoms and course of progression

- 3) Time when the infusion was initiated and time when the infusion reaction began
- 4) Intervention, timing, and subject response
- 5) Time of symptom resolution

Infusion reactions are generally not considered to be DLT, but this judgement should be conducted after each case. Severe (Grade 3 or 4) reactions should be reported within 24 hours to the Sponsor.

Grade 1 infusion reaction (Mild reaction; no infusion interruption or intervention necessary)

Monitor the subject closely or treatment according to the local practise. Consider prophylactic medication (e.g., paracetamol a.k.a. acetaminophen and diphenhydramine) for next administration.

Grade 2 infusion reaction (Moderate reaction leading to infusion interruption but responsive to symptomatic treatment): Interrupt the infusion but maintain vascular access with normal saline. Paracetamol (a.k.a. acetaminophen) and diphenhydramine (or other antihistamine according to local practises) usage is recommended or treatment according to the local practise. However, diphenhydramine (50 mg) and ranitidine (50 mg diluted in 5% dextrose to 20 mL) given together for anaphylaxis are superior to diphenhydramine given alone. Vital sign assessment should be periodically repeated until the subject is stable. Once the symptoms are totally resolved, the infusion may be restarted at maximum 50% of the previous infusion rate. If the symptoms do not recur during 30 minutes of infusion of this slower rate, the infusion rate may be increased to the normal rate. If symptoms recur, the infusion must be stopped, and the amount infused should be reported. Prophylactic medication for the next administration is highly recommended and the infusion rate should be adjusted (see [Section 8.2.1](#) and [Section 8.2.2](#)).

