15.3.4.3 Pharmacokinetic Parameters

The serum concentration of FP-1305 will be determined by a validated method according to the assessment schedules. The concentrations will be summarized by visit and the sampling time using descriptive statistics by the dose level. Only subjects who have received the whole dose at each infusion will be used for the repeated PK analysis. The mean concentration will be plotted against the scheduled sampling times. A tabulated summary with descriptive statistics will be given.

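### The Part II DLT-evaluability rule sets no minimum share of the assigned first dose, so a subject with a partial first infusion and no DLT can count towards clearing a new dose level

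*Protocol*

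**What the plan says.** Four parts of the plan bear on this.

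- **When a first infusion ends early.** Protocol 8.2.1 gives two triggers: "If the subject's symptoms do not resolve within 3 hours, the administration of FP-1305 should be discontinued for this cycle", and "If a second infusion reaction develops despite a reduced infusion rate, the administration of FP-1305 should be discontinued for this cycle". Section 8.9.1 adds, for Grade 2 reactions: "If symptoms recur, the infusion must be stopped, and the amount infused should be reported". Sections 8.9 and 8.9.1 stop the drug permanently after a Grade 3 or 4 infusion reaction.
- **Which reactions are DLTs.** Protocol 4.1 requires Grade 3 or higher and then makes exceptions: "Grade 3 infusion reactions that resolve within 8 hours from the onset of the reaction are not defined as a DLT". Grade 4 acute infusion-related reactions are DLTs. So are Grade 3 reactions that slowing or interrupting the infusion, or supportive care, cannot resolve. Section 8.9.1 says infusion reactions are generally not DLTs but are to be judged case by case.
- **Who is evaluable.** Protocol 4.3.2: "DLT evaluable subject will have at least one dose of IMP and have at least 28 days of follow-up after IMP infusion". A subject who fails this is replaced. A further replacement sentence concerns incomplete follow-up only. Protocol 15.1 defines a DLT population for Part I alone. SAP Part II section 8 takes the first three recruited, or six after one DLT, and names no exposure condition.
- **What evaluability decides.** The second and third sentinel subjects each wait until those before them have 28 days without a DLT. "Once three evaluable subjects have received at least one dose and have been followed up at for 28 days with no DLTs", the rest of the level may enrol without a hold. Under 4.3.1 a level passes with no DLT in three subjects or at most one in six.

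**The concern.** The 3+3 decision at 30, 45 and 100 mg/kg rests on three to six subjects. A subject who received a small part of the assigned dose says little about its tolerability, yet counts like a fully dosed subject if no DLT follows. The sentinel step has the same weakness: its purpose is to see one subject through 28 days at the new dose before exposing the next.

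The situation is foreseeable. Section 8.8 places typical onset of infusion reactions 30 minutes to two hours after the start, mostly at the first or second exposure. Section 2.2.2 gives an infusion time of about 40 to 120 minutes. Reactions therefore tend to fall during the infusion that opens the DLT window. Tolerability of new doses by DLT is a Part II primary outcome.

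**Working it through.** **Step 1: trace two subjects through the rules.**

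*Subject A, recurrent Grade 2 reaction.* The infusion is stopped (8.9.1). The event is below Grade 3, so it is not a DLT (4.1). After 28 days the subject has had some of the drug and full follow-up. Nothing in 4.3.2 or SAP Part II section 8 removes or replaces this subject. Cycle 2 is due at about Day 22, inside the window, but 4.3.2 does not require it.

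*Subject B, Grade 3 reaction that resolves with supportive care in, say, 6 hours.* It is not a DLT (4.1). The drug is permanently discontinued (8.9, 8.9.1), so there is no Cycle 2. The follow-up visit falls 4 weeks, plus or minus 1 week, after the last dose (8.5), so 28 days can be reached. A Cycle 2 delay of more than 14 days for drug-related toxicity would be a DLT, but on Q3W that threshold is 21 + 14 = 35 days after the first infusion, outside the 28-day window.

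On the plain reading, both can count as DLT-free at the assigned level.

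**Step 2: effect on the pass probability.** The plan states no operating characteristics for the Part II 3+3 rule, so there is no figure to reproduce. Inputs:

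- Pass rule (4.3.1): 0 DLTs in 3, or 1 in 3 followed by 0 in the next 3.
- True DLT rate p: 20% is the Part I target (Protocol section 4); 30%, 40% and 50% are illustrative. All are assumptions for Part II.
- k of the first three subjects are truncated and assumed to have zero DLT risk. This is extreme, so the results are upper bounds.

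With q = 1 − p:

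P(pass) = q^(3−k) + (3−k) · p · q^(2−k) · q³

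At p = 0.20:

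- k = 0: 0.512 + 3(0.2)(0.64)(0.512) = 0.512 + 0.197 = 0.709
- k = 1: 0.64 + 2(0.2)(0.8)(0.512) = 0.64 + 0.164 = 0.804

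At p = 0.30:

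- k = 0: 0.343 + 3(0.3)(0.49)(0.343) = 0.343 + 0.151 = 0.494
- k = 1: 0.49 + 2(0.3)(0.7)(0.343) = 0.49 + 0.144 = 0.634

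| True DLT rate | k = 0 | k = 1 | k = 2 |
|---|---|---|---|
| 20% | 0.71 | 0.80 | 0.90 |
| 30% | 0.49 | 0.63 | 0.80 |
| 40% | 0.31 | 0.46 | 0.69 |
| 50% | 0.17 | 0.31 | 0.56 |

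**Step 3: how partial a partial dose could be.** The infusion starts at 50 mL/h for 30 minutes (8.2.1), which is 25 mL. At 25 mg/mL undiluted (8.1.1) that is 25 × 25 = 625 mg. For an assumed 70 kg subject (range 50 to 100 kg), an infusion stopped at 30 minutes has delivered at most:

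- 30 mg/kg: 625/2,100 = 30% (21 to 42%)
- 45 mg/kg: 625/3,150 = 20% (14 to 28%)
- 100 mg/kg: 625/7,000 = 9% (6 to 12.5%)

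Dilution in saline lowers these shares; a later stop raises them. Stopping after a second reaction means more was given than at the first. The figures illustrate scale only.

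**The case against.** The strongest objection is textual. Protocol 15.1 admits subjects to the safety population on any quantity of drug, whereas 4.3.2 asks for one dose, which could mean a complete dose. On that reading a truncated subject would be replaced. This stands as a possible reading: a reader might infer that the protocol positively counts any fraction as a dose, and the documents do not say that. They do not say the opposite either. Where completeness is required, the plan spells it out: "Only subjects who have received the whole dose at each infusion will be used for the repeated PK analysis". SAP Part II section 8 has no dose wording for Part II to interpret.

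Second, a reader might infer that any infusion reaction escapes the DLT definition. That is wrong. Grade 4 reactions and unresolved Grade 3 reactions are DLTs, and each case is judged individually. The route that ends dosing without a DLT is narrow.

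Third, there are safeguards. Cycle 2 at about Day 22 restores some exposure for subjects with a lower-grade reaction, so zero risk overstates the effect. Ten subjects must be enrolled at 30 and at 45 mg/kg before the next level (4.3). Section 4.2.5 has a delayed-toxicity halt rule. The DMC verifies DLTs and reviews toxicity. All of this softens the consequence, but none of it sets an exposure condition, and formal DLT evaluability stops at the first three or six subjects.

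Fourth, a reader might extend the point to the infusion limit in 8.7: "the maximum amount of FP-1305 in one IMP infusion is 10 g and cannot be exceeded irrespective of the weight-based dose". It does not extend. The cap is a declared part of the regimen, so a capped subject has received the full protocol dose.

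**Conclusion.** The point holds as a gap in the evaluability definition, and closing it is a cheap improvement. One dose is undefined, no minimum share is set in Protocol 4.3.2 or SAP Part II section 8, and the infusion rules foresee incomplete first infusions that are often not DLTs. As written, a level can be cleared partly on subjects who did not receive it.

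The size is modest and uncertain. With one truncated subject among the first three, the pass probability rises by at most about 0.10 at a 20% true DLT rate (0.71 to 0.80) and 0.14 at 30% (0.49 to 0.63). This assumes zero DLT risk in that subject, full-dose risk in all the others, and rates not stated for Part II. The larger shifts at 40% and 50% should not be read as the expected effect: the documents support no such rates, and the Part I SAP reports no DLT in 30 subjects. Nor do they give a frequency of truncation, so the overall effect on the escalation cannot be estimated.

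**What to change.** In Protocol 4.3.2 and SAP Part II section 8, state that:

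1. a subject without a DLT is evaluable for the 3+3 count only if at least a given share of the assigned Cycle 1 dose was infused, the sponsor fixing that share in advance;
2. a subject with a DLT is evaluable whatever amount was received;
3. any other subject is replaced for the 3+3 count, still counts towards the cohort of ten, and is listed with the amount infused.

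A dose limited by the 10 g cap counts as the full assigned dose. The change concerns who is counted and leaves dosing and the handling of reactions untouched.

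The cost is wording in two documents. Volume infused and interruptions are already recorded (8.2), and replaced subjects already count towards the ten (4.3.2), so the cohort does not grow. The downside is an occasional extra 28-day wait for a replacement.

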8.2.2 Subsequent Infusions

- Subsequent infusions may be administered at the highest rate that was well tolerated in the preceding cycle, for the first 30 minutes
- In the absence of a hypersensitivity reaction, the infusion rate can be doubled every 30 minutes, to the maximum infusion rate allowed for the dosing level as per instructions given in the Pharmacy Manual
- If a hypersensitivity reaction develops, subjects will be pre-medicated prior to each treatment cycle with:
 - Acetaminophen 1000 mg per os 12 h and 30 min prior to the planned infusion time
 - Antihistamine (Diphenhydramine 50 mg equivalent) per os 12 h and 30 min prior to the planned infusion time
 - Glucocorticoid (Hydrocortisone 100 mg equivalent) I.V. 30 min prior to the planned infusion time
- Variance based on institutional practice is acceptable once discussed with the Sponsor. In addition, the guidelines under First Infusion ([Section 8.2](#)) should be followed for the first subsequent infusion.

After the second infusion (Cycle 2), the Part I subjects and in Part II the first three subjects testing new doses or dosing frequencies must be monitored for safety at the clinical facility for a minimum of 6 hours. Other subjects in Part II and subjects in Part III must be monitored for safety for a minimum of 2 hours after the second infusion.

After Cycle 2 the IMP may be administered in the outpatient setting and the subjects must be monitored for safety for a minimum of 2 hours prior to discharge until the end of the treatment. In any part of the trial, post-dose observation will be longer if deemed appropriate.

8.3 Treatment Schedule

The treatment period is divided into cycles. Each cycle in Q3W dosing lasts three weeks (21 days). The IMP will be administered on Day 1 of each cycle (Q3W) for up to one year with the possibility to extend the treatment beyond one year according to routine clinical practice (see [Section 8.7.1](#)). If the IMP infusion cannot be administered as scheduled the IMP infusion must be administered as soon as possible. The IMP administration day is counted as Day 1 of the cycle (for delays see [Section 8.7](#)).

Protocol Addendum implements more frequent dosings (Q2W and Q1W). Protocol Addendum requires all relevant national approvals in the countries concerned prior to implementation.

8.4 Assessments during Treatment Period

The assessments during the trial are described in the following chapters and also in [Table 1](#) (Part I), [Table 2](#) (Part II) and [Table 3](#) (Part III). Before each IMP administration, a pre-dose physical evaluation is conducted. AEs will be collected during the whole treatment period starting after the signing of the Informed Consent.

8.4.1 Parameters Collected during Pre-Dose Evaluation in Part I

In Part I the pre-dose assessment is done in every cycle for the 1 -year treatment period if not otherwise stated. Pre-Dose assessments maybe taken also up to three days before the Day 1 in each cycle.

- Height (only in Cycle 1)
- Weight
- Vital signs (blood pressure, heart rate, body temperature and respiratory rate).
- A physical examination covering the major body systems (general appearance, head [ear, nose and throat], cardiovascular, eyes, respiratory, abdomen, urogenital, musculoskeletal, neurological, lymph nodes and skin)
- ECG (in Cycles 1, 2, 4, 6, and every second cycle thereafter; the ECG must be performed also always if clinically indicated)
- ECOG performance status
- Urine dipstick test
- PK sampling (only in Cycles 1, 2, 3, 4 and 5)
- Anti-drug antibody (ADA) sampling (on Cycles 1, 2, 4, 6, and every second cycle thereafter, or if clinically indicated)
- Blood samples
 - CBC
 - CMP
 - Endocrine panel (cortisol, lipase, amylase (pancreas specific) in Cycles 1, 4 and 8; thyroid stimulating hormone, PTH, free thyroxine (T4), free triiodothyronine (T3) on each cycle)
 - Hepatitis B and C virus (quantitative assessment in Cycles 1, 2, 4 and 6 if tested initially positive)
 - LDH
 - LDL
 - AFP (HCC subjects)
 - CRP
 - CA-125 (OC subjects)
 - CA19-9 (PDAC, gallbladder cancer, cholangiocarcinoma subjects)
 - CEA (CRC subjects)
- Research blood samples
 - Receptor occupancy and monocytes (RO assay) (only in Cycles 1, 2, 3, and 4)
 - OxLDL (only in Cycles 1, 2, 3, and 4)
 - Flow cytometry (TBNK cells and CD127 FOXP3 Assay) (only in Cycles 1, 2, 3, and 4)
 - Cytokine and chemokine panel (only in Cycles 1, 2, 3, and 4)
 - Blood sample for PBMC isolation (only in Cycles 1 and 4)
- Imaging

- MRI/CT (The same imaging method (CT, MRI) per subject must be used throughout the trial. The first scan (C1) must be less than 6 weeks old prior the first dose (routine diagnostic image can be used). Cycles 1, 4, 7, 10, and every third cycle thereafter, up to one year. The images have to be taken as close as possible (\pm 10 days) to the initial schedule even if there are missed IMP doses. If the treatment extends beyond one year, 18- (\pm 1 month) and 24- (\pm 1 month) month images from the first dose are mandatory to take if not routinely taken at these timepoints.)
- AE assessment; photographs to document visible AEs should be considered
- Concomitant medications and interventional procedures (including herbal products)

